ACO Established	MSSP: July, 2012 AdvocateCare (Commercial): 2011	MSSP: January, 2014 Cigna (Commercial): April, 2013 Anthem (Commercial): July 2013
Location	Illinois	Senior ACO (MSSP): CA, FL, NV Commercial ACO: Greater Los Angeles, CA, NV (Cigna)
Patient population	MSSP: 106,000 Commercial: 370,000	Senior (MSSP): 56,689 Commercial: 65,739
ACO Contract Lives	MSSP: 106,000 Commercial: 370,000	Senior (MSSP): 56,689 Commercial: 65,739

PRINCIPAL INVESTIGATOR (LAST, FIRST, MIDDLE): [name]

Patient Race/Ethnicity	57% Non-Latino White 22% African American 8% Latino 5% Other/multi-racial 3% Asian/Filipino 1% American Indian/Alaska Native 1% Middle East 1% Eastern Indian 2% Unknown/Declined	
 55% Latino 25% Non-Latino White 15% Asian/Pacific Islander 10% African-American 	CLINIC/PRACTICE SELECTION Advocate ACO and HealthCare Partners ACO have 150 and 69 primary care practice sites, respectively. Using the list of PA&E activity domains previously described (see Appendix I for a draft of the checklist instrument), we will randomly select four practices from each ACO that score in the top quartile of the PA&E activities and four practices from each ACO that score in the bottom quartile. This will maximize the difference between those practices with high involvement and those with little or no involvement.
Payer Mix	
 Commercial: 70% Medicare Advantage: 5% Advocate Employee: 5% Medicare ACO: 20% 	
 HCP commercial: 68% HCP Medicaid: 13% HCP Senior: 19% 	
ACO Risk Arrangement	
 Shared savings (no risk) 	
 Shared savings (no risk) 	

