We will categorize the more than 150 Advocate ACO primary care practice sites and the 69 HCP ACO practice sites as high vs. low PA&E involvement based on a brief 40-item practice assessment of the six domains of PA&E activities (see Appendix I). This list was developed in consultation with a National Advisory Committee to our study of ACO involvement in PA&E and the preliminary results of the survey (see page 2) supported by the Gordon and Betty Moore Foundation. This checklist instrument, including measures of the degree of implementation, will be completed by the person most knowledgeable about each practice's PA&E activities. Based on past experience this will be the Chief Medical Officer or Quality Improvement leader. Each of the ACOs practices will be categorized into quartiles based on their overall PA&E score. We will then sample practices for involvement from the top and bottom quartiles to finalize four highly involved PA&E practices and four low involved PA&E practices within each of the two ACOs for engagement in the research study.

Patient Activation (PAM)

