Aim 5. To explore key capabilities of practice teams that might account for their greater involvement in PA&E activities to engage patients and the resulting impact on outcomes of care;

Analyses Addressing Aim 5. For these exploratory analyses, we will use a range of analytic techniques to assess the extent to which changes in team factors impact changes in PA&E activities, including multilevel regression modeling of the quantitative study data and comparative case study analyses of the multiple data sources. For example, we will triangulate the quantitative results with site visit data about the changes to PA&E activities, including treating PA&E as a continuous variable (0 to 40 on our index of activities) occurring at the practices that might explain increases or declines in the outcome measures and primary care teamwork.

$$PA \& E = Team + PracticeSize + Casemix + \varepsilon$$

We will explore an overall teamwork composite, but will also examine differences in effect sizes using the various team subscales assessed in the survey (e.g., relational coordination, team participation, team culture).

Aim 6. To explore the team feedback process to assess the extent to which feedback was used and could explain changes in team-related influences over time.

Analyses Addressing Aim 6. We will use comparative case analyses to compare data feedback processes and teamwork factors at the 16 practices as they relate to improvements in PROs and patient experience over time^{81, 82}.

PRINCIPAL INVESTIGATOR (LAST, FIRST, MIDDLE): [name]

CRITERION 3 – TECHNICAL MERIT (Also see Research Plan and Analysis Plan under Section C. Study Design or Approach.)

D. Project Milestones

Table 3. Project Milestones and Timeline

0-6 months	7-12 months	13-18 months	19-24 months	25-30 months	31-36 months
Wave 1 PA&E Survey Finalize enrollment of practice sites	Site feedback on wave 1 PA&E survey		Wave 2 PA&E Survey	Site feedback on wave 2 PA&E survey	

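### Aim 5 makes the PA&E score the outcome in practices chosen for extreme PA&E scores, so a real wave 1 team effect would be overstated, by about 1.5 to 1.8 times if the true correlation is 0.2 to 0.5

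*Combined protocol and SAP*

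**What the plan says.** Under Clinic/Practice Selection, the investigators will "randomly select four practices from each ACO that score in the top quartile of the PA&E activities" and four "that score in the bottom quartile". The stated purpose is to widen the contrast: "This will maximize the difference between those practices with high involvement and those with little or no involvement". Measurement of Site PA&E Activities repeats the rule. Practices are "categorized into quartiles based on their overall PA&E score", taken from the 40-item site checklist, and "We will then sample practices for involvement from the top and bottom quartiles to finalize four highly involved PA&E practices" plus four low ones in each ACO. The middle half of practices is never sampled.

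In the Analysis Section, the Aim 5 equation has PA&E on the left-hand side and reads "E = Team + PracticeSize + Casemix" plus error. It carries no change signs, although the Aim 4 equations do. The accompanying text speaks of "treating PA&E as a continuous variable (0 to 40 on our index of activities". It also says that the sizes of effect of the team subscales will be compared. The lead sentence of the same paragraph, however, describes changes in team factors acting on changes in PA&E. The aim is labelled exploratory. No correction for the selection, and no statement of it as a limitation, appears in the text.

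**The concern.** Selecting units on a predictor leaves a linear slope unbiased. Selecting them on the extremes of the outcome does not, because the outcome's variance is stretched and its covariance with every predictor of it is stretched too. In Aim 5 the outcome is the score that decided which practices entered.

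The reported slope of PA&E on teamwork would then describe the sampling scheme as well as the practices. A reader would take it as the PA&E gain that goes with a better team score in ACO practices generally, and it would be too large. R-squared is affected in the same direction. What is at stake is the size of the effects in a secondary, exploratory aim, including the planned comparison of subscales.

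**Working it through.** **Inputs from the documents.** Sampling pools of 150 and 69 sites; four practices from the top and four from the bottom quartile in each ACO; 16 practices in total; practice-level analysis; PA&E as a continuous outcome. The documents give no expected coefficient, power or team-PA&E correlation for Aim 5, so there is no stated figure to reproduce.

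**Assumptions.** Team score and PA&E score are standardized and bivariate normal with correlation r. Since r is unknown, a range is shown.

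**Step 1: variance of PA&E after selection.** The cut point is c = z(0.75) = 0.6745. The variance ratio is

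K = 1 + 2·c·φ(c)/0.5 = 1.857.

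**Step 2: slope of PA&E on team score after selection, relative to the population slope.**

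Ratio = K / (1 + (K − 1)·r²)

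| assumed r | large-sample ratio | uniform PA&E score (K = 1.75) | simulated design, 16 practices |
|---|---|---|---|
| 0.2 | 1.80 | 1.70 | 1.88 |
| 0.3 | 1.72 | 1.64 | 1.83 |
| 0.4 | 1.63 | 1.56 | 1.74 |
| 0.5 | 1.53 | 1.47 | 1.62 |
| 0.7 | 1.31 | 1.28 | 1.36 |

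The last column comes from 6,000 simulated studies per value of r. Each draws 4 high and 4 low practices from pools of 150 and 69 and fits least squares with one further, unrelated practice covariate. If practice size or casemix also explains PA&E, r² in the denominator becomes the R² of the whole model and the ratio falls.

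**Step 3: R-squared.** After selection, R² = r²·K / (1 + (K − 1)·r²). At r = 0.3 this is 0.09 × 1.857 / 1.077 = 0.155, against a population value of 0.09.

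**Step 4: no true association.** At r = 0 the simulated mean slope is 0 and the rejection rate is 4.9% at a nominal 5%.

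**Step 5: subscales fitted one at a time.** True standardized slopes of 0.5 and 0.2 would read 0.5 × 1.53 = 0.77 and 0.2 × 1.80 = 0.36. The order is kept. The gap widens from 0.30 to 0.41, while the ratio shrinks from 2.5 to about 2.1.

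**Step 6: other readings of Aim 5.** This step assumes a team-score stability of 0.7, a stability of the unexplained part of PA&E of 0.5 to 0.9, and r = 0.3 or 0.5. Wave 2 levels then give ratios of 1.20 to 1.48, and change on change gives 1.03 to 1.19.

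**Step 7: the model turned round.** With PA&E as predictor, covariance and predictor variance are both multiplied by K, so the slope is r·K/K = r and the ratio is 1.00 for any r. With the high/low group as predictor, practices are drawn at random within each quartile, so the difference in team means estimates the top-versus-bottom-quartile difference directly. R² is not repaired. With continuous PA&E it stays at 0.155 at r = 0.3, because correlation is symmetric; with the two-level group it is about 0.135.

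**The case against.** The best reply is that Aim 5 concerns change. Its lead sentence says so, and for change on change the inflation is slight. That limits the size given here to wave 1 levels. It does not remove the point, because the printed equation is in levels, the Aim 1 analysis text promises the cross-sectional relation of PA&E and teamwork at each wave, and Table 3 places the integration of PA&E and teamwork results alongside the analysis of wave 1 data.

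A second reply is that the recommended direction is partly planned already. The opening statement of the research question promises to describe teams in high and low practices. The Aim 5 sentence on the continuous index goes on to treat PA&E as something that might explain outcomes and teamwork. This is fair: the group comparison is not foreign to the plan, and Aim 5 also uses comparative case studies. But the only equation printed for Aim 5 runs the other way.

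Third, with 16 practices imprecision rivals the bias. At r = 0.3 the bias is about 0.3 × 0.72 = 0.22, against a simulated standard deviation of the slope of 0.33. At r = 0.5 it is about 0.5 × 0.53 = 0.27, against 0.24. That stands, but a wide interval around a biased value does not correct the value.

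A reader might infer that the team findings would be spurious, or that the main comparison is compromised. Neither follows. The selection creates no association when the true slope is zero, and in Aim 1 PA&E is the explanatory variable, for which sampling the extremes is a reasonable design. Nor do the documents say that Aim 5 coefficients will be carried into guidance: they speak of guidance in general, and tie the development of guidelines to the site visits.

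**Conclusion.** The point holds for the model as printed, fitted to wave 1 levels. A non-zero team slope would be overstated by about 1.5 to 1.8 times for r between 0.2 and 0.5 with a roughly normal PA&E score, and by about 1.3 at r = 0.7. Neither r nor the shape of the score is given in the documents. A uniform score gives only slightly smaller factors, so normality is not decisive.

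A flat statement that Aim 5 inflates team effects by 1.5 to 1.8 times would go too far, since the factor depends on r, on the wave, and on whether levels or changes are analysed. Labelling the aim exploratory limits the consequence but does not correct the coefficient. The change is worth making because the unbiased comparison uses data already planned.

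**What to change.** For the cross-sectional part of Aim 5, replace the equation with:

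team score (composite, then each subscale) = high/low PA&E group + ACO + practice size,

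adding casemix only as far as 16 practices allow. An intercept and three one-parameter terms already leave 16 − 4 = 12 residual degrees of freedom. Report the adjusted mean difference with its confidence interval, and label it a top-versus-bottom-quartile contrast. Do not present R-squared or standardized effects as population values, since turning the model round does not correct them.

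A logistic model for high versus low is only a secondary option, because separation is likely to be a problem with 8 practices per group. Weighting is no remedy: the middle quartiles have no chance of selection.

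Reconcile the levels equation with the Aim 5 text, and write the change analysis with change terms as in Aim 4.

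The cost is a changed equation and a few sentences, with no new data. The downside is that the result is a difference between groups, not PA&E points per unit of team score.

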Through practice-based research and dissemination of evidence, The Center for Healthcare Organizational and Innovation Research (CHOIR), directed by [name] and Associate Director [name], aspires to help make the U.S. healthcare system among the most responsive in the world, characterized by high quality, efficient, and patient-centered care. CHOIR currently has approximately \$8 million of extramural funding across 8 concurrent projects. CHOIR faculty and staff are located together centrally on the UC Berkeley campus to facilitate communication.

Health Research for Action (HRA) Center at UC Berkeley

Health Research for Action is one of the UCB School of Public Health's initiatives to translate research findings into successful resources and programs for the public. The HRA Director of Research is [name], MD, MHSA. The Center works with communities, foundations, and government agencies to reduce health and health care disparities and create more hopeful, empowered communities through research-driven health promotion services and programs. The Center's resources and programs have reached over ten million people in the United States and around the world.

Office

The offices of the faculty of the SPH CHOIR are situated in University Hall on the UC Berkeley campus. Library and conference facilities are also available in University Hall, as well as other support facilities, including mail, fax, photocopying, and IT support.

Other

All the support services of a major University campus are available to this project: library, computer center, materials management, accounting, business and financial services, and human resources.

PRINCIPAL INVESTIGATOR (LAST, FIRST, MIDDLE): [name]

G. Research Engagement Plan

CRITERION 5 - PATIENT AND STAKEHOLDER ENGAGEMENT

There will be a patient advisory group at each study site that will actively participate in all aspects of the research including the development of instruments, assessment and review of findings throughout the study, making recommendations for improvement of practices' PA&E activities, and assisting in dissemination and implementation of findings. In addition, at least two prominent patient engagement advocates ([name] and [name]) are included on our overall study advisory committee. They will help to insure that the study design, and analysis stays focused on the patient-centered study aims. They will also assist in the dissemination of study findings.

Importance of Patient-Centered Approaches:

This proposal reflects the importance of examining patient-centered approaches for their potential to improve patient-reported outcomes of care and related clinical measures. Patient Centered Outcomes Research (PCOR) recognizes the expertise of patients, families, and community health organizations as collaborators in research, and has emerged as an increasingly important approach in conducting health services research projects. We can leverage the expertise of patients, including underserved patient populations, to help guide development, implementation and feedback of our measures and findings; the patient advisory groups will address these issues. We believe this participatory approach will be key to successful study implementation and yield important, high quality patient-centered health services research findings.^{83, 84}

Plan for meaningful engagement of patients:

As previously indicated we include patient advisory group input throughout the study. Our goal is to have the patient advisory groups provide input in the first few months of the study with these groups to then meet 2-3 times annually and to undertake tasks that will include, but not be limited to: input into research design, instrumentation, review of preliminary results, interpretation of those results, and advising on dissemination of results.

Further, this proposal has been informed by years of research involving health care teams and their patients and most recently from interviews with patients and caregivers on our related preliminary study of ACO Patient Activation and Engagement funded by the Gordon and Betty Moore Foundation.

Experience in Patient and Stakeholder Engagement:

[name] is currently the PI on the study funded by the Moore Foundation to assess what ACOs are currently doing in regard to PA&E activities, and to identify some of the barriers and facilitators to further involvement. In addition to the survey which has been informed by patient input, the study team is making two site visits, interviewing patients and their caregivers to learn more about what appears to be working and not working in regard to PA&E.

[name] and her colleagues at Health Research for Action have many years of experience using participatory processes in research projects. Nearly every research project at HRA contains a community advisory board, and for those projects based within clinical sites, includes a group of patient advisors. Our work in this proposal will benefit from this experience.

As noted above we will draw on our overall study advisory committee and the site-specific patient advisory groups. We will ask for direct input from the site-specific patient groups in the first few months of the study with a goal for these advisory groups to meet 2 to 3 times annually and to undertake tasks that will include, but not be limited to: input into research design, instrumentation, review of preliminary results, interpretation of those results, and advising on dissemination of results.

PRINCIPAL INVESTIGATOR (LAST, FIRST, MIDDLE): [name]

DISSEMINATION AND IMPLEMENTATION POTENTIAL

Describe the potential for disseminating and implementing the results of this research in other settings.

There is great potential for disseminating and implementing the results of this research in other settings due to the established relationships which we have with many stakeholders in the field. This includes, but is not limited to: 1) All of the ACOs throughout the country through the ongoing work funded by the Commonwealth Fund; 2) through serving on the Advisory Board ([name]) of the Kaiser-Permanente Institute for Health Policy that convenes roundtables and other dissemination forums for the results of such research; 3) in California, through our leadership of the Right Care Initiative focusing on reducing strokes and CVD in San Diego, Sacramento, and Los Angeles through greater patient and provider engagement; and 4) through our ties to the CDC Million Hearts campaign. All of this is in addition to the usual publication of study findings in journals, and at conferences and professional meetings. We look forward to working with PCORI on an overall dissemination and implementation strategy and determining the necessary resources involved.

Describe possible barriers to disseminating and implementing the results of this research in other settings.

There are two major barriers to disseminating and implementing the results of this research in other settings. The first is the challenge of adapting the study results to new and different contexts; the “we are different – it will never work here” challenge. The second is having sufficient time and resources to spread the study results to other settings. If the current proposal is funded and the results are promising, we look forward to submitting a subsequent dissemination proposal to be considered which will address our approach to these issues.

PRINCIPAL INVESTIGATOR (LAST, FIRST, MIDDLE): [name]

REPRODUCIBILITY AND TRANSPARENCY OF RESEARCH

Describe the ability to reproduce potentially important findings from this research in other data sets and populations.

As large scale delivery systems begin to form and as electronic health records become more prevalent it becomes more possible for organizations like Advocate Health Partners and HealthCare Partners to work with their patient populations to improve process and outcomes of care. The instruments from our study can be made available to other delivery systems to conduct such research in addition to what we learn about the role of patient activation and engagement in the research process.

PROTECTION OF HUMAN SUBJECTS

PROTECTION OF HUMAN SUBJECTS – University of California, Berkeley

Risks to Human Subjects

Human Subjects Involvement, Characteristics, and Design

This research seeks to determine whether patients with diabetes or cardiovascular diseases (CVD) who receive care from provider practices affiliated with accountable care organizations (ACOs) with high involvement in patient activation and engagement (PA&E) experience better patient-reported outcomes, better experience of care, and improved clinical process measures compared with adult patients with diabetes or CVD who receive care from teams with low involvement in PA&E activities. These and related chronic conditions represent an estimated 75 percent of all U.S. health care expenditures.¹⁴ In addition, we will examine: (1) whether this effect is stronger for patients who score higher on the patient activation measure (PAM) than those who do not¹⁰; and (2) whether this effect is stronger for patients who improve their PAM scores over time than for those who do not. We will also assess the characteristics of practice teams associated with both high and low involvement in PA&E activities in regard to their degree of relational coordination, perceived team effectiveness, leadership, and team culture that they exhibit. Finally, we will examine the impact of feeding back the T1 patient outcome and teamwork assessment results to both caregivers and patient advisory groups on subsequent T2 measures of both patient outcomes and teamwork assessments.

We will engage patients and primary care teams within two ACOs. The two selected to participate in this research are Advocate Health in Chicago, Illinois and HealthCare Partners in Torrance, California. Within each ACO, we will select four practices that are highly involved in PA&E and four that are less or not at all involved. We will make this determination based on a broad definition of PA&E activities that will include: (1) patient care outreach in regard to disease prevention and health promotion; (2) changes in the clinician-patient relationship, particularly in the areas of communication, motivational interviewing, and involvement in treatment care plans; (3) shared decision-making; (4) patient self-management of their condition(s); (5) end of life/advanced serious illness care patient engagement and family involvement; and (6) patient involvement in the overall design of care and in organization-wide efforts to improve the quality of care.

From among those practices we will select 273 patients with diabetes and/or CVD from each of eight practices at each ACO – a total of four practices with high involvement in PA&E and four practices with low PA&E involvement. Given two ACOs, we will have data from 4,368 patients with these chronic conditions. We will follow them as cohorts over a two-year period. We will obtain measures of blood pressure, HbA1c and LDL-C at 12 months and 24 months from the EHR. Patients selected for the study will be mailed a survey including the 13-item PAM measure at baseline (0-3 months). Patients will complete patient-reported outcomes (PROMIS) and experience of care measures between 7-12 months and again at between 19-24 months. Patients who do not complete and return the survey by mail will be contacted by phone (up to 8 attempts) and offered an opportunity to complete the questions by computer-assisted telephone interview (CATI). We will survey and follow-up with patients in both English and Spanish, according to their stated primary language preference. Patients will be offered a \$20 incentive to complete the survey by mail or by CATI. The calculations provided below for the PROMIS self-reported measures and for blood pressure provide evidence of sufficient statistical power to detect meaningful differences between practices on these key variables of interest.

To project the sample size requirements given 16 practices (8 high PA&E and 8 low PA&E), we estimated the design effect (DE) to account for the clustering of patients within practice sites. While PROMIS data from participating ACO patients are presently unavailable, recent studies of change over time on the PROMIS physical functioning measure informed our sample size estimates for the PROMIS measure⁴⁷. Having been selected using item-response theory (IRT) methods and extensive testing, the PROMIS physical functioning measure is a precise measure that is sensitive to small changes in physical functioning over time.

Quantum Market Research, a survey firm in Oakland, CA, will be hired to administer the patient survey. Given the published estimates and a range of design effect estimates (intraclass correlation (ICC)=0.01-0.04) to account for the clustering of patients within practices, a clinically meaningful change (a 3-5 point change out of 100) on the PROMIS physical functioning measure can be detected with 50-65 patients per practice. Based on prior experience, we expect a minimum 50% response rate for completing the first patient survey and a 65% response rate for the second survey. We

PRINCIPAL INVESTIGATOR (LAST, FIRST, MIDDLE): [name]

expect a 3% undeliverable addresses and a 20% drop out rate between the two survey periods based on our previous research. Patient-level blood pressure data from adult diabetic patients at HealthCare Partners practices were used to calculate the design effect (ICC=0.01-0.02). Previous research suggests that population-level improvements in blood pressure on the order of 3-5mm Hg are clinically meaningful.^{48, 49} Based on a two-sided difference of means with a power of 0.90, we estimate that an average of 140 patients per practice are needed to detect a 3 mm Hg difference in change in systolic blood pressure over time between the high (n=8) vs. low (n=8) PA&E practices. Based on these calculations, we will randomly select 273 patients per practice (n=4,368) with diabetes or CVD diagnoses from each of the practice sites and teams in the two ACOs for inclusion in the study. Given the assumptions of response rates and attrition noted above, this will yield a final total of 1102 patients with two time points for analysis of the PROMIS (69 patients per site). In addition we expect to receive retrospective clinical outcomes data for all sampled patients (n=4,368) from the electronic health record. Thus, even with slightly lower than expected survey response rates, our study will be sufficiently powered to detect clinically meaningful differences between high and low PA&E practices on both patient-reported (PROMIS) and clinical, e.g., blood pressure, outcome measures.

Two site visits to each of the two ACOs will be conducted at two points in time to gain an insight to the strategic goals of the ACOs in improving patient activation and engagement and fostering high functioning interdisciplinary primary care teams: (1) during the 0-6 month start-up phase of the study, and again (2) during the period of 18-24 months.

Sources of Materials

Patients selected for the study will be mailed a survey including the 13-item PAM measure, patient-reported outcomes (PROMIS), and experience of care measures between 7-12 months and again between 19-24 months. Please see Appendix III for examples of questions to be included in the patient survey. We will obtain measures of blood pressure, HbA1c and LDL-C at 12 months and 24 months from the EHR at Advocate Health and HealthCare Partners.

Advocate Health and HealthCare Partners will be responsible for linking patients' EHR data to their study ID, and thus the data transmitted will not be identifiable to any researchers or staff at UC Berkeley. All such de-identified data will be housed at Berkeley on password-protected, secure servers accessible only by Principal Investigator [name] and the Co-Investigators and staff under his direction.

Quantum Market Research (QMR) will be responsible for contacting patients to complete the survey. They will receive identifiable patient information such as name, address, and phone number directly from Advocate and HealthCare Partners only for the purposes of administering the survey.

Primary care team members from each of the 16 practices will complete the following instruments that we refer to as "teamwork assessment instruments." These are: (1) team culture, (2) team leadership, (3) relational coordination, and (4) perceived team effectiveness. These will be completed at baseline (0-3 months) and then again at 18 months. UC Berkeley will manage and administer the staff survey.

Only the Investigators at Advocate and Health Care Partners site will have the key linking survey data to names of their own patients completing the survey. No investigators at UC Berkeley or Dartmouth or staff on the project besides the ACOs will have access to a key allowing linkage of collected data to identifiable patient information.

Potential Risks

There are no physical, financial, or legal risks to patients selected for participation in this project. The principal risks from this study concern the potential for loss of confidentiality.

With respect to the site visits and staff surveys performed at the 16 ACO practices, the information collected through the survey and in-depth interviews with physicians and other ACO executives pertains to each organization's professional activities only and does not pertain to any personal matters. The collection of these survey data do not pose any physical, financial, or legal risks to the ACO practice team members.

Adequacy of Protection Against Risks

Recruitment and Informed Consent

Informed consent will be obtained from all selected patients before completion of the survey. A written consent letter will be included with the mailed surveys and phone consent will be specifically obtained at the beginning of each follow-up CATI interview.

PRINCIPAL INVESTIGATOR (LAST, FIRST, MIDDLE): [name]

Informed consent will also be obtained from the team members surveyed during administration by UC Berkeley investigators.

Protections Against Risk

To minimize the risk of loss of confidentiality, all information with the potential to identify study participants will remain housed at Advocate Health and Health Care Partners, respectively, only accessible to Advocate Health and HealthCare Partners staff.

Potential Benefits of the Proposed Research to Human Subjects and Others

Patients may benefit from the feedback of the time one findings which could enable some of the practice sites to make changes which directly benefit some patients subsequent to time 2. Furthermore, the knowledge gained from this study at the participating ACOs could potentially benefit all enrolled patients. As large scale delivery systems begin to form and as the electronic health record becomes more prevalent, it becomes more possible for organizations to work with their patient populations to improve process and outcomes of care. The instruments from our study can be made available to other delivery systems to conduct such research in addition to what we learn about the role of PA&E in the research process.

Importance of the Knowledge to be Gained

This research is important as relatively little is known about the impact of actively engaging patients on such outcomes of care. Further, there are major gaps in knowledge and understanding of what practice team characteristics are associated with achieving better outcomes from more fully engaged patients. Thus the research is directly relevant to practices working on PA&E as well as payers and policy makers interested in encouraging engagement. The risk of the loss of confidentiality combined with the planned procedures to minimize that risk are reasonable in relation to the importance of the knowledge that is reasonably expected to result from this study.

INCLUSION OF WOMEN AND MINORITIES

Detailed Study Enrollment Table

Racial Categories	Not Hispanic or Latino		Hispanic or Latino		TOTAL
	Female	Male	Female	Male	
American Indian/ Alaska Native	11	11	0	0	22
Asian	178	171	0	0	349
Native Hawaiian or Other Pacific Islander	11	11	0	0	22
Black or African American	356	342	0	0	699
White	913	878	702	674	3167
More than One Race	56	54	0	0	109
TOTAL	1526	1466	702	674	4368

INCLUSION OF CHILDREN

Individuals under 18 will be excluded from the proposed research as the chronic adult conditions proposed for study for this project are not relevant to children.

PROTECTION OF HUMAN SUBJECTS – Dartmouth College

Risks to Human Subjects

Human Subjects Involvement, Characteristics, and Design

The investigators at Dartmouth College will participate in the design of the research and will participate in the site visits to Advocate Health care and HealthCare Partners to interview practice staff, as described above.

PRINCIPAL INVESTIGATOR (LAST, FIRST, MIDDLE): [name]

Sources of Materials

Dartmouth will not be participate in the selection of patients and will receive de-identified data only after the conclusion of data collection. No Dartmouth investigators or staff will have any access to identifiable patient data. Dartmouth will have also have access only to de-identified practice team staff assessment data. Dartmouth will participate in the site visit interviews.

Potential Risks

The information collected by Dartmouth investigators through the in-depth interviews with physicians and other ACO executives pertains to each organization's professional activities only and does not pertain to any personal matters. Data collected will be maintained confidentially. The collection of these data do not pose any physical, financial, or legal risks to the ACO practice team members.

Recruitment and Informed Consent

Consent will be obtained from all ACO practice staff prior to beginning site visit interviews.

Protections Against Risk

The collection of the site visit interview data does not pose any physical, financial, or legal risks to the ACO practice team members. Nevertheless names of interviewees will be kept confidential and will not be made public.

Potential Benefits of the Proposed Research to Human Subjects and Others

Data gained and summarized in feedback reports from the site visits may benefit Advocate Health Care and HealthCare Partners by enable some of the practice sites to make changes which directly the delivery of care at these organizations.

Importance of the Knowledge to be Gained

Please see above under Protection of Human Subjects – UC Berkeley.

INCLUSION OF WOMEN AND MINORITIES

Please see above under Protection of Human Subjects – UC Berkeley.

INCLUSION OF CHILDREN

Please see above under Protection of Human Subjects – UC Berkeley.

PROTECTION OF HUMAN SUBJECTS – Advocate Health Care and HealthCare Partners

Risks to Human Subjects

Human Subjects Involvement, Characteristics, and Design

Protection of human subjects considerations are identical for the two ACOs participating in this project. Advocate Health Care and HealthCare Partners will each securely transmit names, addresses, and contact information for adult patients with diabetes and/or cardiovascular diseases with at least 2 visits in the baseline year (2013) from each of eight primary care practices affiliated with our Accountable Care Organization (ACO) to the patient survey vendor selected for the project, Quantum Market Research. The four primary managerial and supervisory staff members at the survey firm have all completed the Collaborative Institutional Training Initiative (CITI) modules relating to Human Subjects Protection training, as have a number of other QMR staff, including interviewers. Although all QMR employees have followed strict procedures with regard to human subjects throughout their careers, this formalizes the training.

The two ACOs will also securely transmit a de-identified patient-level data to the UC Berkeley research team in Months 7 and 19 covering 2014 and 2015 period, respectively. The dataset will include adult patients with diabetes, cardiovascular disease, and/or asthma with at least 2 visits in the baseline year (2014) and the data elements include select sociodemographic information and clinical care process and outcome data using Healthcare Effectiveness Data Information Set (HEDIS) definitions for measures of chronic illness care.

PRINCIPAL INVESTIGATOR (LAST, FIRST, MIDDLE): [name]

For analysis of all patient-level data at UC Berkeley, we will create unique subject identifiers that do not include date of birth, social security number, or medical record number. The ACOs will be responsible for linking each patient's EHR data to their study ID, and thus the data transmitted will not be identifiable to any researchers or staff at UC Berkeley. All such de-identified data will be housed at Berkeley on password-protected, secure servers accessible only by Principal Investigator [name] and the Co-Investigators and staff under his direction.

Advocate Health Care and HealthCare Partners will also provide the UC Berkeley research team with the names, emails, and mail contact information for all primary care clinicians and staff of the eight practices so that a survey of team culture, leadership, relational coordination, and perceived team effectiveness can be conducted at two points in time (between months 0-6 and between months 13-18).

These two ACOs will also work with the UC Berkeley team to coordinate two site visits lasting two to three days for the research team to interview key people, some patients, and to observe meetings. Finally, the ACOs will assist with recruiting five patient representatives from the target population to serve on an advisory board that will provide recommendations and feedback for the ACO practices to consider as they refine and improve their PA&E efforts.

Sources of Materials

Advocate Health and HealthCare Partners will be responsible for linking patients' EHR data to their study ID, and thus the data transmitted will not be identifiable to any researchers or staff at UC Berkeley.

As described above, Quantum Market Research (QMR) will receive identifiable patient information such as name, address, and phone number directly from Advocate and HealthCare Partners only for the purposes of administering the survey.

